4.3 Eligibility Criteria

Patients must have baseline evaluations performed prior to the first dose of study drug and must meet all inclusion and exclusion criteria. In addition, the patient must be thoroughly informed about all aspects of the study, including the study visit schedule and required evaluations and all regulatory requirements for informed consent. The written informed consent must be obtained from the patient prior to enrollment. The following criteria apply to all patients enrolled onto the study unless otherwise specified.

4.3.1 Inclusion Criteria

Patients eligible for this study will be those with melanomas that are BRAF/NRAS wild-type and that have an oncogenic kinase fusion. Patients who have received at least one

FDA-approved line of therapy for unresectable/metastatic melanoma are eligible. Patients who are treatment-naïve but who refuse available standard options and prefer to enroll on study as their first line of treatment after a thorough informed consent process will be eligible for this study at the discretion of the treating physician.

Further inclusion criteria vary depending on the basket to which the patient will be assigned. Please refer to the drug-specific appendices for further details on inclusion criteria.

- For patients with MET fusion to be treated with capmatinib, see Appendix 6, Section 6.1.
- For patients with ALK fusion to be treated with ceritinib, see Appendix 7, Section 7.1.
- For patients with RET or BRAF fusion to be treated with regorafenib, see Appendix 8, Section 8.1.
- For patients with NTRK1, NTRK2, NTRK3, or ROS1 fusion to be treated with entrectinib, see Appendix 9, Section 9.1.

4.3.2 Exclusion Criteria

Exclusion criteria vary depending on the basket to which the patient will be assigned. Please refer to the drug-specific appendices for further details on exclusion criteria.

- For patients with MET fusion to be treated with capmatinib, see Appendix 6, Section 6.2.
- For patients with ALK fusion to be treated with ceritinib, see Appendix 7, Section 7.2.
- For patients with RET or BRAF fusion to be treated with regorafenib, see Appendix 8, Section 8.2.
- For patients with NTRK1, NTRK2, NTRK3, or ROS1 fusion to be treated with entrectinib, see Appendix 9, Section 9.2.

4.4 Duration of Therapy

Subjects may discontinue study treatment or withdraw their consent to participate in the study at any time without prejudice. The Investigator may withdraw a subject from study treatment or from the study if, in his or her clinical judgment, it is in the best interest of the subject or if the subject cannot comply with the protocol. In addition, any of the following conditions require discontinuation of the subject from study treatment:

- Disease progression.
- An AE or inter-current illness that in the opinion of the Investigator warrants the subject's withdrawal from study.

- If the subject does not recover from his or her toxicities to tolerable Grade ≤ 2 within 6 weeks, the subject will have study treatment discontinued unless there is unequivocal evidence that the subject is benefitting. In this situation, a subject may be able to restart therapy with a dose reduction upon resolution of the toxicity.
- Inability to tolerate the lowest dose of study drug as detailed in Table 2.
- Women who become pregnant or are breastfeeding.
- Sexually active subjects who refuse to use medically accepted barrier methods of contraception (e.g., male or female condom) during the course of the study and for 4 months after discontinuation of study treatment.
- Necessity for treatment with other anti-cancer treatment prohibited by protocol.
- Request by regulatory agencies for termination of treatment of an individual subject or all subjects under the protocol.
- Significant patient non-compliance with protocol.

4.5 Duration of Follow Up

Patients will be followed until death or removal from study, whichever occurs first.

5 Study Drugs

- Capmatinib – See Appendix 6
- Ceritinib – See Appendix 7
- Regorafenib - See Appendix 8
- Entrectinib – See Appendix 9

5.1 Drug Accountability

The Investigational Pharmacist will manage drug accountability records. Accurate records of receipt of all study drugs will be kept, including dates of receipt. In addition, accurate records will be kept regarding when and how much study treatment is being dispensed and used by each subject in the study. Reasons for deviation from the expected dispensing regimen must also be recorded. At completion of the study, to satisfy regulatory requirements regarding drug accountability, all unused study drug will be reconciled and destroyed in accordance with applicable state and federal regulations.

5.2 Drug Ordering

UCSF will obtain capmatinib, ceritinib, regorafenib and entrectinib directly from their respective pharmaceutical companies as study supply.

5.3 Packaging and Labeling of Study Drugs

Drugs will be packaged and labeled per UCSF institutional standards, adhering to applicable local and federal laws.

6 Treatment Plan

Patients will be treated with an appropriate kinase inhibitor as outlined in Table 1. Cycle length is defined for this study as 4 weeks. Patients will be restaged every 2 cycles (8 weeks), and best objective response will be confirmed using RECIST v1.1 with measurements at a minimum of 4 weeks after the response-defining determination. Dose reductions and dose interruptions for management of toxicity will be specified in the sections below.

6.1 Dosage and Administration

Treatment will be administered on an outpatient basis. See Table 2 for dosage and administration information.

Table 2. Drug Regimens

Study Drug	Precautions	Start Dose	Dose Level -1	Dose Level -2	Dose Level -3	Route	Schedule	Cycle Length
Capmatinib	Do not take with food (do not eat at least 1 hour before or 2 hours after drug ingestion)	400 mg	300 mg	200 mg	N/A	PO	BID	28 days
Ceritinib	Take with low-fat meal	450 mg	300 mg	150 mg	N/A	PO	Once daily	28 days
Regorafenib	Take each morning with a low-fat breakfast	160 mg	120 mg	80 mg	N/A	PO	Once daily (21 days on, 7 days off)	28 days
Entrectinib	Take within 1 hour following a meal	600 mg	400 mg	200 mg	N/A	PO	daily	28 days

7 Study Procedures and Observations

7.1 Schedule of Procedures and Observations

The study-specific assessments are detailed in this section. Screening assessments must be performed within 30 days prior to the first dose of investigational product except for the staging which can be done 90 days prior. Any laboratory results falling outside of the reference ranges may be repeated at the discretion of the investigator. All on-study visit procedures are allowed a **window of ± 7 days** unless otherwise noted. Treatment or visit delays for public holidays or weather conditions do not constitute a protocol violation. Additional follow-up visits may be added and additional tests ordered per discretion of treating Investigator.

A written, signed, informed consent form (ICF) and a Health Insurance Portability and Accountability Act (HIPAA) authorization must be obtained before any study-specific assessments are initiated. A copy of the signed ICF will be given to the subject and a copy will be filed in the medical record. The original will be kept on file with the study records.

All patients who are consented will be registered in OnCore[®], the UCSF Helen Diller Family Comprehensive Cancer Center (HDFCCC) Clinical Trial Management System (CTMS). The system is password protected and meets HIPAA requirements.

7.1.1 Pretreatment and Treatment Period

In addition to the assessments outlined in the study calendars, the following will be performed within 30 days before the Day 1 visit.

- Documentation of measureable disease
- History of prior treatments and any residual toxicity relating to prior treatment
- Determination of baseline medications taken within 30 days of Day 1
- Serum Hepatitis assessment, including Hepatitis B surface antigen (HBsAg), Hepatitis B surface antibody (HBsAb), Hepatitis B core antibody (HBcAb), Hepatitis C antibody
- Serum HIV test

7.1.2 Long Term/Survival Follow-up Procedures

Follow-up history to be conducted by phone call, otherwise per standard of care for metastatic melanoma and PI discretion.

7.1.3 Discontinuation of Therapy

The Investigator will withdraw a patient whenever continued participation is no longer in the patient's best interests. Reasons for withdrawing a patient include, but are not limited to, disease progression, the occurrence of an adverse event or a concurrent illness, a patient's request to end participation, a patient's non-compliance or simply significant uncertainty on the part of the Investigator that continued participation is prudent. There may also be administrative reasons to terminate participation, such as concern about a patient's compliance with the prescribed treatment regimen.

8 Reporting and Documentation of Results

8.1 Evaluation of Efficacy (or Activity)

Evaluation of efficacy to be assessed by ORR and CBR, using RECIST v1.1 criteria.

Response and progression in this study will be evaluated using the new international criteria proposed by the Response Evaluation Criteria in Solid Tumors ([RECIST](#)) Committee²⁸. Changes in only the largest diameter (unidimensional measurement) of the tumor lesions are used in the RECIST v1.1 criteria. Local review of response or progression will be performed at each site. Data for each patient with a response will be reviewed at UCSF.

Definitions

Evaluable for toxicity

All patients will be evaluable for toxicity from the time of their first treatment with the study drug.

Evaluable for objective response

Only those patients who have measurable disease present at baseline, have received at least one cycle of therapy (with at least 90% of intended dosing administered during cycle 1), and have had their disease re-evaluated will be considered evaluable for response. These patients will have their response classified according to the definitions stated below. (Note: Patients who exhibit objective disease progression prior to the end of Cycle 1 will also be considered evaluable.)

Disease Parameters

Measurable disease

Measurable disease is defined as the presence of at least one measurable lesion by radiographic assessment or by clinical examination (e.g., skin lesion). If the measurable disease is restricted to a solitary lesion, its neoplastic nature should be confirmed by cytology/histology. Positive bone scans and radiographic studies of bone involved with tumor are not considered to be measurable disease.

All tumor measurements will be recorded in millimeters or decimal fractions of centimeters. Previously irradiated lesions are considered non-measurable except in cases of documented progression of the lesion since the completion of radiation therapy.

Target lesions

These techniques should be performed with cuts of 10 mm or less in slice thickness contiguously. Spiral CT should be performed using a 5 mm contiguous reconstruction algorithm. This applies to tumors of the chest, abdomen, and pelvis.

Cytology, Histology

These techniques can be used to differentiate between partial responses (PR) and complete responses (CR) in rare cases (e.g., residual lesions in tumor types, such as germ cell tumors, where known residual benign tumors can remain).

The cytological confirmation of the neoplastic origin of any effusion that appears or worsens during treatment when the measurable tumor has met criteria for response or stable disease is mandatory to differentiate between response or stable disease (an effusion may be a side effect of the treatment) and progressive disease.

8.1.1.1 Response Criteria**Evaluation of Target Lesions****Complete Response (CR)**

Disappearance of all target lesions, determined by two separate observations conducted not less than 4 weeks apart. Any pathological lymph nodes (whether target or non-target) must have reduction in short axis to < 10 mm (the sum may not be “0” if there are target nodes). There can be no appearance of new lesions.

Partial Response (PR)

At least a 30% decrease in the sum of the longest diameter (LD) of target lesions, taking as reference the baseline sum LD. There can be no appearance of new lesions.

Progressive Disease (PD)

At least a 20% increase in the sum of the SLD of target lesions, taking as reference the smallest sum SLD recorded since the treatment started and minimum 5 mm increase over the nadir, or the appearance of one or more new lesions.

Stable Disease (SD)

Neither sufficient shrinkage to qualify for PR nor sufficient increase to qualify for PD taking as reference the smallest sum LD since the treatment started. Patients having a documented response with no reconfirmation of the response will be listed with stable disease.

Evaluation of Non-Target Lesions

Complete Response (CR)

Disappearance of all non-target lesions and normalization of tumor marker level. If tumor markers are initially above the upper normal limit, they must normalize for a patient to be considered in complete clinical response.

Incomplete Response/Stable Disease (SD)

Persistence of one or more non-target lesion(s) and/or maintenance of tumor marker level above the normal limits.

Progressive Disease (PD)

Appearance of one or more new lesions and/or unequivocal progression of existing non-target lesions. Although a clear progression of “non-target” lesions only is exceptional, in such circumstances, the opinion of the treating physician should prevail

Evaluation of Best Overall Response

The best overall response is the best response recorded from the start of the treatment until disease progression/recurrence (taking as reference for progressive disease the smallest measurements recorded since the treatment started). The patient's best response assignment will depend on the achievement of both measurement and confirmation criteria.

Table 3. Response Criteria

Target Lesions	Non-Target Lesions	New Lesions	Overall Response	Best Response for this Category Also Requires
CR	CR	No	CR	> 4 weeks confirmation
CR PR	Non-CR/ Non-PD Non-PD	No No	PR PR	> 4 weeks confirmation
SD	Non-PD	No	SD	documented at least once > 4 weeks from baseline
PD Any Any	Any PD* Any	Yes or No Yes or No Yes	PD PD PD	no prior SD, PR or CR

* In exceptional circumstances, unequivocal progression in non-target lesions may be accepted as disease progression

Patients with a global deterioration of health status requiring discontinuation of treatment without objective evidence of disease progression at that time should be reported as “symptomatic deterioration”. Every effort should be made to document the objective progression even after discontinuation of treatment.

The best overall response for an early death, i.e., a patient who dies without documentation of disease progression and before it was time to conduct the first tumor reassessment, will be considered inevaluable or not assessed adequately. Response will also be considered inevaluable for any patient receiving treatment (regardless of how much was received) who did not have any follow-up assessment completed before initiation of alternative treatment.

In some circumstances it may be difficult to distinguish residual disease from normal tissue. When the evaluation of complete response depends upon this determination, it is recommended that the residual lesion be imaged by PET scan or be investigated by fine needle aspirate/biopsy before confirming the complete response status.

Duration of Response

Duration of overall response

The duration of overall response is measured from the time measurement criteria are met for CR or PR (whichever is first recorded) until the first date that recurrent or progressive disease is objectively documented (taking as reference for progressive disease the smallest measurements recorded since the treatment started).

The duration of overall CR is measured from the time measurement criteria are first met for CR until the first date that recurrent disease is objectively documented.

Duration of stable disease

Stable disease is measured from the start of the treatment until the criteria for progression are met, taking as reference the smallest measurements recorded since the treatment started.

Progression-Free Survival

Progression-free survival (PFS) is defined as the duration of time from start of treatment to time of progression.

Evaluation of Safety

Analyses will be performed for all patients having received at least one dose of study drug. The study will use the [CTCAE v4.03](#) for reporting of non-hematologic adverse events and modified criteria for hematologic adverse events.

For multicenter studies, the Principal Investigator at the UCSF Coordinating Center will hold the role of Study Chair. The Study Chair is responsible for the overall conduct of the study and for monitoring its safety and progress at all participating sites.

8.3 Definitions of Adverse Events

8.3.1 Adverse Event

An adverse event (also known as an adverse experience) is defined as any untoward medical occurrence associated with the use of a drug in humans, whether or not considered drug related. More specifically, an adverse event (can be any unfavorable and unintended sign (e.g., an abnormal laboratory finding), symptom, or disease temporally associated with the use of a drug, without any judgment about causality. An adverse event can arise from any use of the drug (e.g., off-label use, use in combination with another drug) and from any route of administration, formulation, or dose, including an overdose.

8.3.2 Adverse Reaction

An adverse reaction is defined as any adverse event caused by the use of a drug. Adverse reactions are a subset of all suspected adverse reactions for which there is reason to conclude that the drug caused the event.

8.3.2.1 Suspected

A suspected adverse reaction is defined as any adverse event for which there is a reasonable possibility that the drug caused the adverse event. For the purposes of IND safety reporting, “reasonable possibility” indicates that there is evidence to suggest a causal relationship between the drug and the adverse event. A suspected adverse reaction implies a lesser degree of certainty about causality than an adverse reaction.

8.3.2.2 Unexpected

An adverse event or suspected adverse reaction is considered *unexpected* if it is not listed in the investigator brochure or package insert(s), or is not listed at the specificity or severity that has been observed, or, if an investigator brochure is not required or available, is not consistent with the risk information described in the general investigational plan or elsewhere in the current application.

“Unexpected,” as used in this definition, also refers to adverse events or suspected adverse reactions that are mentioned in the investigator brochure as occurring with a class of drugs or as anticipated from the pharmacological properties of the drug, but are not specifically mentioned as occurring with the particular drug under investigation.

Adverse events that would be anticipated to occur as part of the disease process are considered *unexpected* for the purposes of reporting because they would not be listed in the investigator brochure. For example, a certain number of non-acute deaths in a cancer trial would be anticipated as an outcome of the underlying disease, but such deaths would generally not be listed as a suspected adverse reaction in the investigator brochure.

Some adverse events are listed in the Investigator Brochure as occurring with the same class of drugs, or as anticipated from the pharmacological properties of the drug, even though they have not been observed with the drug under investigation. Such events would be considered *unexpected* until they have been observed with the drug under investigation. For example, although angioedema is anticipated to occur in some patients exposed to drugs in the ACE inhibitor class and angioedema would be described in the investigator brochure as a class effect, the first case of angioedema

observed with the drug under investigation should be considered *unexpected* for reporting purposes.

8.3.2.3 Serious

An adverse event or suspected adverse reaction is considered *serious* if, in the view of either the investigator or sponsor, it results in any of the following outcomes:

- Death
- Life-threatening adverse event
- Inpatient hospitalization or prolongation of existing hospitalization
- A persistent or significant incapacity or substantial disruption of the ability to conduct normal life function
- Congenital anomaly/birth defect

Important medical events that may not result in death, are life-threatening, or require hospitalization may be considered serious when, based upon appropriate medical judgment, they may jeopardize the patient or subject and may require medical or surgical intervention to prevent one of the outcomes listed in this definition. Examples of such medical events include allergic bronchospasm requiring intensive treatment in an emergency room or at home, blood dyscrasias or convulsions that do not result in inpatient hospitalization, or the development of drug dependency or drug abuse.

8.3.2.4 Life-threatening

An adverse event or suspected adverse reaction is considered *life-threatening* if, in the view of either the investigator or sponsor, its occurrence places the patient or subject at immediate risk of death. It does not include an adverse event or suspected adverse reaction that, had it occurred in a more severe form, might have caused death.

8.4 Recording of an Adverse Event

All grade 3 and above adverse events will be entered into OnCore[®], whether or not the event is believed to be associated with use of the study drug. Data about these events and their severity will be recorded using the NCI CTCAE v4.03.

The Investigator will assign attribution of the possible association of the event with use of the investigational drug, and this information will be entered into OnCore[®] using the classification system listed below:

Relationship	Attribution	Description
Unrelated to investigational drug/intervention	Unrelated	The AE is clearly NOT related to the intervention
	Unlikely	The AE is doubtfully related to the intervention
Related to investigational drug/intervention	Possible	The AE may be related to the intervention
	Probable	The AE is likely related to the intervention
	Definite	The AE is clearly related to the intervention

Signs or symptoms reported as adverse events will be graded and recorded by the Investigator according to the CTCAE. When specific adverse events are not listed in the CTCAE they will be graded by the Investigator as *none, mild, moderate* or *severe* according to the following grades and definitions:

Grade 0	No AE (or within normal limits)
Grade 1	Mild; asymptomatic or mild symptoms; clinical or diagnostic observations only; intervention not indicated
Grade 2	Moderate; minimal, local, or noninvasive intervention (e.g., packing, cautery) indicated; limiting age-appropriate instrumental activities of daily living (ADL)
Grade 3:	Severe or medically significant but not immediately life-threatening; hospitalization or prolongation of hospitalization indicated; disabling; limiting self-care ADL
Grade 4:	Life-threatening consequences; urgent intervention indicated
Grade 5:	Death related to AE

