2.2 Secondary Objectives

- To estimate tumor stability in melanoma patients treated with kinase inhibitors matched to the tumor-specific fusion kinase.
- To estimate survival in melanoma patients treated with kinase inhibitors matched to the tumor-specific fusion kinase.
- To examine the safety and tolerability of kinase inhibitors in patients with melanoma with a fusion kinase.

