8.6 Adverse Events Monitoring

All adverse events, whether or not unexpected, and whether or not considered to be associated with the use of the study drug, will be entered into OnCore®, as noted above.

The Investigator will assess all adverse events beginning at the time of informed consent and determine reportability requirements to the UCSF Data and Safety Monitoring Committee (DSMC) and UCSF's Institutional Review Board, the Institutional Review Board (IRB); and, when the study is conducted under an Investigational New Drug Application (IND), to the Food and Drug Administration (FDA) if it meets the FDA reporting criteria.

All adverse events entered into OnCore® will be reviewed by the Helen Diller Family Comprehensive Cancer Center Site Committee on a weekly basis. The Site Committee will review and discuss at each weekly meeting the selected toxicity, the toxicity grade, and the attribution of relationship of the adverse event to the administration of the study drug(s).

All grade(s) 3-5 adverse events entered into OnCore® will be reviewed on a monthly basis at the Site Committee meetings. The Site Committee will review and discuss the selected toxicity, the toxicity grade, and the attribution of relationship of the adverse event to the administration of the study drug(s).

In addition, all suspected adverse reactions considered "serious" entered into OnCore®, will be reviewed and monitored by the Data and Safety Monitoring Committee on an ongoing basis and discussed at DSMC meetings, which take place every six weeks.

For a detailed description of the Data and Safety Monitoring Plan for a Multicenter Phase 2 or 3 Institutional Study at the Helen Diller Comprehensive Cancer Center please refer Appendix 4 Multicenter Institutional Studies.

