A 2-stage optimal design will be employed in which a 10% response rate is considered not promising, a 30% response rate is considered promising, and the probabilities of a type I error (falsely accepting a non-promising therapy) and type II error (falsely rejecting a promising therapy) are set at 0.05 and 0.1, respectively. In this scenario, the maximum trial size would be 35 evaluable patients. Evaluable patients would be those with baseline staging, treatment for at least one cycle (with at least 90% of intended doses administered during cycle 1), and at least one post-baseline staging scan while on treatment. We estimate a drop-out rate of 20%, and therefore 44 patients will be enrolled and started on treatment. In the first stage of this design, 11 patients will be accrued. If 1 or fewer patients achieve a response among the initial 11 patients, the trial will be terminated. If at least 2 patients achieve a response among these 11 patients, then an additional 24 patients will be accrued to the second stage. If 6 or fewer patients achieve a response in the second stage, the trial will be terminated. Under these conditions, if the response rate is 0.1, the probability of ending the trial during stage 1 is 0.70. If the true response rate is 0.3, the probability that the trial will be stopped in stage I is 0.11.

Analysis of study results will be carried out by the study statistician and will include overall response rate (ORR) estimations of ALK, NTRK, ROS1, RET, MET, and BRAF rearrangement-positive patients.

Clinical benefit rate (CBR) defined as the proportion of patients achieving a complete response (CR) or partial response (PR) or stable disease (SD) for > 24 weeks will be estimated for each arm along with a 95% confidence interval.

Progression free survival (PFS) defined as the time from treatment start to the progression or death and overall survival defined as the time from treatment start to death will be estimated using Kaplan-Meier methodology.

Frequencies of toxicities will be tabulated according to CTCAE v4.03 to assess drug safety and tolerability.

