Adverse events reporting to the DSMC will include reports from both the UCSF Coordinating Center, as well as the participating sites. The DSMC will be responsible for monitoring all data entered in OnCore® at the UCSF Coordinating Center and the participating sites. The data (i.e. copies of source documents) from the participating sites

will be faxed over to the UCSF Coordinating Center prior to the monitoring visits in order for the DSMC to monitor the participating site's compliance with the protocol, patient safety, and to verify data entry.

Adverse Event Review and Monitoring

All grade(s) 3-5 adverse events, whether or not unexpected, and whether or not considered to be associated with the use of the study drug, will be entered into OnCore®, UCSF's Clinical Trial Management System.

All Grade 3-5 adverse events entered into OnCore® will be reviewed on a monthly basis at the UCSF Site Committee meetings. All clinically significant adverse events must be reported to the UCSF Coordinating Center by the participating sites within 10 business days of becoming aware of the event or during the next scheduled quarterly conference call, whichever is sooner. The UCSF Site Committee will review and discuss the selected toxicity, the toxicity grade, and the attribution of relationship of the adverse event to the administration of the study drug(s) from the UCSF Coordinating Center and the participating sites.

In addition, all suspected adverse reactions considered "serious" must be entered in OnCore® and reported to the UCSF Coordinating Center within 1 business day. The suspected adverse reactions considered "serious" will be reviewed and monitored by the Data and Safety Monitoring Committee on an ongoing basis and discussed at the DSMC meeting, which take place every six (6) weeks.

If a death occurs during the treatment phase of the study or within 30 days after the last administration of the study drug(s) and is determined to be related either to the investigational drug or any research related procedure, the Study Chair at the UCSF Coordinating Center or the assigned designee must be notified within 1 business day from the participating site(s) and the Study Chair must then notify the DSMC Chair or qualified alternate within 1 business day of this notification. The contact may be by phone or e-mail.

Increase in Adverse Event Rates

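### Sections 8.4 and 8.6 and Appendix 2 set different grade thresholds for entering adverse events in OnCore, so grade 1-2 toxicity may be missing or unevenly captured in the per-drug safety tables

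*Combined protocol and SAP*

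**What the plan says.** Three places in the protocol state which adverse events go into OnCore.

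- Section 8.4: "All grade 3 and above adverse events will be entered into" OnCore, regardless of attribution.
- Section 8.6 has no grade threshold for what goes into OnCore: "All adverse events, whether or not unexpected, and whether or not considered to be associated with the use of the study drug". The sentence then refers back to what was noted earlier, although the earlier text in 8.4 carries the grade 3 threshold.
- Appendix 2, in the plan for multicenter studies, sets the rule for OnCore as follows: "All grade(s) 3-5 adverse events, whether or not unexpected, and whether or not considered to be associated with the use of the study drug".

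Appendix 2 adds a separate duty for participating sites: "All clinically significant adverse events must be reported to the UCSF Coordinating Center by the participating sites within 10 business days", or at the next quarterly call if that is sooner. It does not define clinical significance by grade. It also requires serious suspected adverse reactions to be entered in OnCore and reported within 1 business day, at any grade.

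On the analysis side, one secondary objective is "To examine the safety and tolerability of kinase inhibitors in patients with melanoma with a fusion kinase" (Section 2.2). Section 3.2 makes each inhibitor's adverse effect profile under CTCAE v4.03 a secondary endpoint. Section 9 states: "Frequencies of toxicities will be tabulated according to CTCAE v4.03 to assess drug safety and tolerability". None of the three restricts the grades. Section 10.6 places all study data in OnCore through standardized forms.

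**The concern.** The safety endpoint is written without a grade limit, but two of the three data-entry rules require entry only from grade 3 upward. A site that reads Section 8.4 or Appendix 2 and enters nothing below grade 3 has done what those sections ask. A site that reads Section 8.6 enters everything. The toxicity table for a drug would then depend partly on which section its sites followed.

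This matters because tolerability is a stated objective and all four drugs are oral agents that may be taken until progression. The protocol itself relies on tolerability without a grade cut-off: Section 4.1 chose the ceritinib regimen partly because gastrointestinal events and dose interruptions were fewer with it. By the protocol's own scale in Section 8.4, a grade 2 event can limit instrumental daily activities. Drug groups may also be small, since Section 4.2 aims for at least 5 patients per drug, so differences in site practice could be mistaken for differences between drugs.

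**Working it through.** The plan gives no figure to reproduce, and no power or error-rate formula applies. The check sets the rules side by side and follows them through to the tables.

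| Place | Threshold for OnCore entry | Committee review of entered events |
|---|---|---|
| Section 8.4 | Grade 3 and above | Not stated |
| Section 8.6 | None (all adverse events) | Weekly for all entered events; monthly for grades 3-5 |
| Appendix 2 | Grades 3-5; serious suspected reactions at any grade | Monthly for grades 3-5; no weekly all-event review |

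**Step 1: is there a governing rule?** None is stated. Section 8.6 sends the reader to Appendix 4 for the multicenter monitoring plan, but Appendix 4 covers specimen collection and the plan is in Appendix 2, as Section 10.7 correctly has it. A reader who finds the right appendix meets the grade 3-5 rule, which conflicts with the section that sent them there.

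**Step 2: what does each rule guarantee?**

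- Grades 3-5: required by all three places, so entry does not depend on which one a site follows.
- Serious suspected reactions of any grade: required by Appendix 2.
- Non-serious grade 1-2 events: required by Section 8.6 alone.

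The third group is the only one exposed.

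**Step 3: does the exposed group belong to the planned analysis?** Yes. The objective (2.2), endpoint (3.2) and tabulation (9) have no grade restriction. Since Section 10.6 makes OnCore the study database, an event not entered there is not available to the planned tables.

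**Step 4: size.** The documents give no expected grade 1-2 rate for this population, so the number of events at risk cannot be computed. What can be shown is how sensitive a small drug group is. With n patients on a drug, one patient whose only occurrence of a given toxicity was grade 1-2 and was not entered lowers that drug's observed frequency by 1/n. At the Section 4.2 target minimum of n = 5, this is 1/5 = 20 percentage points. This illustrates sensitivity; it does not predict how often omission would occur.

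**Step 5: patients affected by a fix.** Section 4.2 plans 44 enrolled patients, from 35 evaluable and 20% drop-out (35/0.80 = 43.75, rounded up to 44). It allows up to 50 if enrolment continues to fill the drug groups.

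**The case against.** The strongest reply is that Section 8.4 and Appendix 2 set a floor. Neither excludes lower grades, and a site that enters every event satisfies all three places at once. The pairing in Section 8.6 of a weekly review of all entered events with a monthly grade 3-5 review also suggests that all-grade entry was intended. That is a fair reading of intent, and a reader who infers that grade 1-2 entry is prohibited goes beyond the text. The reply does not remove the conflict, because a site that stops at the floor complies with Section 8.4 and Appendix 2.

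Second, a reader might infer that low-grade events would be lost for good. The documents do not support that. Section 8.4 has the investigator grade and record reported signs and symptoms, Section 8.5 has all adverse events followed until resolved, Section 8.6 has them assessed from consent, and Sections 10.6 and 10.8 require source records and case histories. Grade 1-2 events may well be recoverable from these, but recovery would mean retrospective abstraction across sites.

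Third, it is tempting to say that the weekly committee review could not work under a grade 3 rule. It could: it covers whatever has been entered, and low grades would simply be absent from it.

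Fourth, one database, standardized forms and regular site calls make divergence between sites less likely. That stands as mitigation. However, the text available does not show that the forms require all grades. The drug-specific Appendices 6 to 9 are separate attachments and the study calendars are not in the text, so any collection rule in them could not be checked.

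**Conclusion.** The conflict holds: the three places state different OnCore entry thresholds in current text, and no passage resolves them. The consequence is conditional. If some or all sites stop at grade 3, non-serious grade 1-2 toxicity will be missing from OnCore or captured unevenly, and the per-drug tables will fall short of the unrestricted endpoint.

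The effect is confined to a secondary, descriptive endpoint with no test attached. The primary response endpoint is untouched. A reader might infer that toxicity rates in general would be confounded with site, or that every grade 1-2 event would be absent. Neither follows: grade 3-5 rates rest on a rule common to all three places, and serious suspected reactions are entered at any grade. Nor does Section 9 promise tabulation by grade; it refers to CTCAE v4.03 without giving the layout, which is a reason to specify it.

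The verdict assumes that Appendices 6 to 9, the calendars and the form instructions do not already impose one all-grade rule. Even if they do, the main text should be made to agree with them. Confidence is high on the conflict in wording; how much data would be affected is unknown.

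**What to change.** Amend Section 8.4 and Appendix 2 to match Section 8.6: all sites enter adverse events of every grade in OnCore from informed consent onward, each with its CTCAE v4.03 grade and attribution. Keep the monthly committee review of grades 3-5 as it is. State in Section 9 that toxicities of all grades are tabulated by drug. While editing Section 8.6, correct its pointer from Appendix 4 to Appendix 2.

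If the intention is to collect only grade 3 and above, make that the rule in all three places, and restrict the Section 3.2 safety endpoint and the Section 9 tables to those grades so that the report does not claim a full adverse effect profile.

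The first option costs wording changes and modest extra data entry for about 44 to 50 patients. The change is best made prospectively, because filling in low-grade events later would depend on chart abstraction at each site.
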